## 9.11 Treatment Compliance

Treatment compliance with IP regimens will be assessed by study personnel via capsule counts of returned medication and by questioning the subject, if necessary, at every post-baseline visit. A subject who is not compliant (taken < 80% or > 100% of IP) will be counseled at each visit on

Version: Final Version v4.0 Page 27 of 58

the importance of taking IP as instructed. A subject who is noncompliant on 3 consecutive visits will be discharged from the study.

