# 13.4.2 Exposure and Compliance

Exposure to IP will be summarized for all participating subjects. Subjects will be described with respect to cumulative exposure as well as categorized by the highest dose received.

Compliance with study medication will be determined for each subject. Based on capsule counts, the number of doses administered will be expressed as the proportion of doses scheduled. Compliance will be assessed independently for each phase of the study (ie, dose optimization and maintenance).

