- SCARED Significant School Avoidance is the summation of questions 2, 11, 17, and 36.
- SCARED Total Score is the summation of all 41 questions, each scored from 0 to 2 scale.
- C-SSRS Suicidal Ideation is an indicator of any subject who experience any one of the five suicidal ideation events at least once (Questions 4, 6, 8, 10, and 12)
- C-SSRS Suicidal Behavior is an indicator of any subject who experience any one of the suicidal behavior events at least once (Questions 22, 26, 29, 32, and 35)
- C-SSRS composite endpoint of Suicidal Ideation or Behavior is an indicator of any subject who experiences any one of the ten suicidal ideation or behavior events at least once.
- TEAE An AE is defined as treatment emergent if the first onset or worsening is after the first administration of IP (NFC-1 or placebo) and not more than 7 days after the last administration of IP
- For the tabulation of TEAE's that are related to study drug, these are defined as any TEAE which is determined by the investigator as 'possibly related' or 'related'.
- Post-Treatment AE is an AE that has started more than 7 days after last administration of IP.
- Prior medications are defined as medications or therapies initiated prior to date of first dose of IP and terminating prior to date of first dose of IP. Medications that are started prior to the date of first dose of IP and are continuing after the first dose of IP are considered to be both prior and concomitant medications
- Concomitant medication is defined as any medication a subject received concurrently with study treatment.
- Post-treatment medication is defined as any medication that has started more than 7 days after the last administration of IP.
- Compliance (Overall) = $(\sum (Individual Week Compliance) * (Time-Weight)) * 100. A subject is non-compliant if they take <math>< 80\%$ or > 120% of IP.
 - Individual Week Compliance is defined as the number of capsules taken at a particular week divided by the expected number of capsules taken at a particular week. Given that a subject will be dose optimized, the number of expected capsules will vary according to which dose the subject is currently on for each day.
 - Time-Weight is the fraction of \mathbf{x}/\mathbf{y} where \mathbf{x} is the number of days in the week the subject is expected to be on dose and \mathbf{y} is the whole treatment duration defined as first dose last dose + 1.

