9.8 Exposure and Compliance

For each subject, treatment compliance will be calculated at each visit and summarized for the entire study. Overall compliance will be summarized by treatment group. Compliance is defined in Section 6.3. Drug Accountability/Exposure and Treatment compliance will also be provided in a subject listing.

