<event 1=""></event>	xx (xx x%)	xx (xx.x%)
Potentially Related	xx (xx x%)	xx (xx.x%)
Not Related	xx (xx x%)	xx (xx.x%)
<event 2=""></event>	xx (xx x%)	xx (xx.x%)
Potentially Related	xx (xx x%)	xx (xx.x%)
Not Related	xx (xx x%)	xx (xx.x%)
<event 3=""></event>	xx (xx x%)	xx (xx.x%)
Potentially Related	xx(xxx%)	xx (xx.x%)
Not Related	xx (xx x%)	xx (xx.x%)

Note: Percentages are 100*n/N. Subjects were counted only once for each System Organ Class (SOC) or Preferred Term. If a subject experiences the same event, the event which most related to study drug is used. Any AE determined by the investigator as 'possibly related' or 'related' is considered potentially related for purposes of analysis.

[1] Adverse Events were coded from MedDRA (version xx x).

Source: Listing 16.2.6.1

Table 14.3.1.9
Incidence of TEAEs by Maximum Severity by Randomized Treatment
Safety Population

{Similar shell as Table 14.3.1.8; Source: Listing 16.2.6.1} {Update update first row of table, nest Severity within each category.}

Page 1 of x Final

14.3.2 Summary of Exposure to Study Drug and Compliance by Actual Dose and Randomized Treatment Safety Population

	NFC-1	NFC-1	NFC-1	All	
Variable	100mg	200mg	400mg	NFC-1	Placebo
Statistic	(N=xx)	(N=xx)	(N=xx)	(N=xx)	(N=xx)
Total Drug Exposure (mg)					
n	XX	XX	XX	XX	XX
Mean	XX.X	XX X	XX X	XX X	
Standard Deviation	XX XX	XX.XX	XX.XX	XX XX	
Median	XX.X	XX X	XX X	XX X	
Minimum, Maximum	(x, x)	(x, x)	(x, x)	(x, x)	
Treatment Duration (days) [1]					
n	XX	XX	XX	XX	XX
Mean	XX.X	XX X	XX X	XX X	XX.X
Standard Deviation	XX XX	XX.XX	XX.XX	XX XX	XX XX
Median	XX.X	XX X	XX X	XX X	XX.X
Minimum, Maximum	(x, x)				
Compliance [2]					
n	XX	XX	XX	XX	XX
Mean	XX.X	XX X	XX X	XX X	XX.X
Standard Deviation	XX XX	XX.XX	XX.XX	XX XX	XX XX
Median	XX.X	XX X	XX X	XX X	xx.x
Minimum, Maximum	(x, x)				

^[1] Treatment Duration is defined as Date of Last Dose – Date of First Dose + 1.

Source: Listing 16.2.4.1, 16.2.4.2

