^[2] A subject is non-compliant if they take < 80% or > 100% of IP. Compliance (Overall) = (sum of (Individual Week Compliance) * (Time-Weight)) * 100. Individual Week Compliance is defined as the number of capsules taken at a particular week divided by the expected number of capsules taken at a particular week. Given that a subject will be dose optimized, the number of expected capsules will vary according to which dose the subject is currently on for each day. Time-Weight is the fraction of x/y where x is the number of days in the week the subject is expected to be on dose and is the whole treatment duration.

T:\Medgenics\NFC-1\ADHD-201\...\xxx.sas run on DDMMMYYYY at HH:MM on data extracted on DDMMMYYYY

Protocol: MDGN-NFC1-ADHD-201

Page 1 of x Final

Table 14.3.3.1 Summary of Clinical Laboratory Data: Clinical Chemistry by Randomized Treatment by Study Visit Safety Population

Analyte		
Visit	NFC-1	Placebo
Statistic	(N=xx)	(N=xx)
4. 1. (
<pre><analyte (unit)=""></analyte></pre>		
Baseline		
n	XX	XX
Mean	XX XX	XX XX
Standard Deviation	XX.XXX	XX XXX
Median	XX XX	XX XX
Minimum, Maximum	(x x, x x)	(x x, x x)
Visit 3		
n	XX	XX
Mean	XX XX	XX XX
Standard Deviation	XX.XXX	XX XXX
Median	XX XX	XX XX
Minimum, Maximum	(x x, x x)	(x x, x x)

{Continue for all scheduled post-baseline visits and all analytes. Start a new page for every additional analyte}

Source: Listing 16.2.7.1

Table 14.3.3.2 Summary of Clinical Laboratory Data: Hematology by Randomized Treatment by Study Visit Safety Population

{Similar shell as Table 14.3.3.1; Source: Listing 16.2.7.2}

Table 14.3.3.3 Summary of Clinical Laboratory Data: Urinalysis by Randomized Treatment by Study Visit Safety Population

{Similar shell as Table 14.3.3.1; Source: Listing 16.2.7.3}

Page 1 of x Final

Table 14.3.3.4
Shifts from Baseline of Clinical Laboratory Data: Clinical Chemistry by Randomized Treatment Safety Population

Analyte Visit [1]		NF (N=				Place (N=		
Category	Missing	Low	Normal	High	Missing	Low	Normal	High
<analyte (unit)=""></analyte>								
Visit 3								
Missing	xx(xx.x%)	xx (xx x%)	xx (xx.x%)	xx(xxx%)	xx (xx x%)	xx (xx x%)	xx (xx.x%)	xx (xx x%)
Low	xx (xx.x%)	xx (xx x%)	xx (xx.x%)	xx (xx x%)	xx (xx x%)	xx (xx x%)	xx (xx.x%)	xx (xx x%)
Normal	xx(xx.x%)	xx (xx x%)	xx (xx.x%)	xx (xx x%)	xx (xx x%)	xx (xx x%)	xx (xx.x%)	xx (xx x%)
High	xx (xx.x%)	xx (xx x%)	xx (xx.x%)	xx (xx x%)	xx (xx x%)	xx (xx x%)	xx (xx x%)	xx (xx x%)
Visit 4								

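### The SAP compliance measure has three separate defects: a time-weight denominator that ends at the last dose, no summary by phase, and two different upper limits for non-compliance

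*SAP*

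**What the plan says.** **Formula.** SAP 6.3 defines weekly compliance as "the number of capsules taken at a particular week divided by the expected number of capsules taken at a particular week". Each week is multiplied by x/y and the products are summed. The numerator x "is the number of days in the week the subject is expected to be on dose and" the denominator y "is the whole treatment duration defined as first dose last dose + 1". The minus sign is missing from the text as extracted. Footnote [1] of Table 14.3.2 supplies it: "Treatment Duration is defined as Date of Last Dose – Date of First Dose + 1".

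**Level of summary.** Protocol 13.4.2: "Compliance will be assessed independently for each phase of the study (ie, dose optimization and maintenance"). SAP 9.8 says instead that "treatment compliance will be calculated at each visit and summarized for the entire study". Table 14.3.2 has a single compliance block. Its columns split by dose and treatment, not by phase. The list of changes in SAP Section 10 does not mention compliance.

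**Limits.** SAP 6.3 calls a subject non-compliant below 80% or above 120%. Footnote [2] of Table 14.3.2 and the footnote of Listing 16.2.4.2 both read "A subject is non-compliant if they take < 80% or > 100% of IP". Protocol 9.11 agrees with those footnotes: "A subject who is not compliant (taken < 80% or > 100% of IP) will be counseled".

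**The concern.** The numerator of the weight follows the plan and the denominator follows what the subject did. The two agree when dosing continues to the scheduled end. They part when a subject stops capsules without leaving the study: y shrinks, the planned days do not, and the result is no longer a weighted mean.

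This matters most in the last two weeks. Protocol 7.2 gives the maintenance phase the purpose of letting the drug effect stabilise before the end-of-treatment assessment. A whole-study figure is dominated by the four optimization weeks, so it says little about dosing when the primary endpoint is read. The discharge rule in Protocol 9.11 needs three consecutive non-compliant visits. Maintenance has only Visits 7 and 8, so non-adherence confined to that phase cannot trigger it.

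Non-compliance is one of the deviation categories in SAP 7.2, and major deviations define the PP set in SAP 5. Misleading or contradictory compliance information can therefore reach that review.

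**Working it through.** The documents give no numerical compliance result to reproduce, so the formula was applied to simple dosing patterns.

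**Inputs**
- Phase lengths: 28 + 14 = 42 days (Protocol 10.1.3).
- x = 7 in each of 6 full weeks; y = last dose day − first dose day + 1 (SAP 6.3, Table 14.3.2).
- Overall compliance = 100 × Σ (taken / expected) × (x / y).
- Lower limit 80% (all sources); upper limit 120% (SAP 6.3) or 100% (SAP footnotes, Protocol 9.11).

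**1. Denominator.** Full dosing on Days 1–28, none on Days 29–42, subject attends Visit 8. Then y = 28.
- Weeks 1–4: 4 × 1 × 7/28 = 1.00. Weeks 5–6: 2 × 0 × 7/28 = 0. Overall = 100%.
- Sum of weights: 6 × 7/28 = 42/28 = 1.5, not 1.
- With y = 42: 4 × 7/42 = 66.7%, which is below 80%.

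Other patterns under the same formula:

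| Dosing pattern | SAP 6.3 | y = 42 |
|---|---|---|
| 80% of capsules to Day 28, then none | 4 × 0.8 × 7/28 = 80.0% | 4 × 0.8 × 7/42 = 53.3% |
| Full to Day 31, then none | 31/31 = 100% | 31/42 = 73.8% |
| Full to Day 14, then none | 14/14 = 100% | 14/42 = 33.3% |
| Full to Day 28, none until a full day's dosing on Day 42 | 29/42 = 69.0% | 29/42 = 69.0% |

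The last row shows where the defect ends: one day's dosing at the scheduled end restores y to 42.

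Reading the expected days as also ending at the last dose does not help. Weeks 5–6 would then carry no weight and the weights would sum to 28/28 = 1, but the score would still be 100%.

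**2. Pooling, with y = 42.** Full optimization dosing and a fraction c of maintenance doses give (28 + 14c)/42. Setting this to 0.80 gives c = (33.6 − 28)/14 = 0.40. A subject who takes 40% of maintenance doses sits exactly at 80% and is not flagged. By phase the same subject shows 100% and 40%.

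**3. Upper limit.** A subject at 110% throughout scores 6 × 1.1 × 7/42 = 110%. That is compliant under SAP 6.3, and non-compliant under Table 14.3.2, Listing 16.2.4.2 and Protocol 9.11.

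**The case against.** **The denominator problem is narrow.** It needs complete cessation that lasts to the end, in a subject who is not withdrawn. For a subject who formally discontinues IP early, first to last dose is a sensible period. Protocol 8.3 also lets the investigator withdraw a subject for non-compliance with study procedures. All of this stands. It limits how often the error would occur but does not make the formula right when it does.

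**The information is not lost.** Listing 16.2.4.2 has a by-week column, Listing 16.2.4.1 gives start and end dates for each dose, and Table 14.3.2 shows treatment duration beside compliance. Protocol 9.11 provides for capsule counts and, if necessary, questioning at every post-baseline visit. A reader might infer that the overall score is the trial's only evidence of dosing during maintenance. These sources show that it is not.

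**No planned inference uses the score.** The primary analysis is on the ITT population (SAP 8.1). Deviations are classified case by case (SAP 7.2), PP membership follows a blinded data review (SAP 5), and PP analyses are optional with no planned tables (SAP 6.1). A reader might infer that a false 100% keeps a subject in the PP set. No passage makes the overall score, or any cut-off on it, the PP criterion.

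**The pooling example is a property of any pooled 80% threshold.** That is fair: it is not a formula error. The defect is that the protocol requires the phase split and the SAP does not deliver it. Section 10 claims to list only major changes, so its silence is weak evidence by itself. The missing summary is the point.

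**Conclusion.** The concern holds as three independent defects. It would be tempting to read them as one mechanism, but only the denominator produces the 100% score: 100% passes under either upper limit, and pooling with y = 42 would give 66.7% and flag the subject.

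1. The SAP 6.3 formula gives a wrong value, 100% instead of 66.7%, for a subject who doses fully to Day 28, then stops and stays in the study. This assumes that last dose means the last dose taken, which is the plain reading and matches the Table 14.3.2 footnote.
2. A summary that the protocol requires is missing, and the pooled figure can pass a subject at 40% of maintenance doses.
3. The upper limit contradicts itself within the SAP, and SAP 6.3 contradicts the protocol. Subjects above 100% and up to 120% are classified both ways.

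The effect is confined to the descriptive compliance table and to the information available to the deviation review behind an optional PP set. The documents give no rate for such dosing patterns, so the number of subjects affected cannot be stated.

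**What to change.** - **SAP 6.3 and the matching footnotes:** define y as the total days the subject was expected to be on IP, from first dose to the scheduled end of IP or to formal discontinuation. The weights then sum to 1 and early withdrawals are not penalised. The time-weighting can stay.
- **SAP 9.8 and Table 14.3.2:** add one compliance row for the optimization phase and one for the maintenance phase, as Protocol 13.4.2 requires, and give both to the blinded deviation review. Neither document sets a PP cut-off on these values, and this correction does not need one.
- **Upper limit:** reconcile SAP 6.3, the footnotes of Table 14.3.2 and Listing 16.2.4.2, and Protocol 9.11. The sponsor must decide which limit is intended.

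The cost is SAP wording, two table rows and some reprogramming. Capsule counts are already collected at every post-baseline visit. Reported compliance may be slightly lower, and a few more subjects may be flagged for review.

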6.4 Adjustment for multiple comparisons

There will be no adjustments for multiple comparisons in the analysis.

SAP FINAL Version 2.0

7 STUDY PATIENTS/SUBJECTS AND DEMOGRAPHICS

7.1 Disposition of Subjects and Withdrawals

All subjects who provide informed consent will be accounted for in this study. The number of subjects screened, randomized, completing, and withdrawing from the study, as well as reason for withdrawal, will be summarized by treatment group, dose, and overall. Additionally, the number of subjects in each population will be displayed. All disposition information will be included in a listing.

Page 15 of 88

7.2 Protocol Deviations

Protocol deviations will be collected by the clinical team and provided to biostatistics prior to database lock. Protocol deviations will be reviewed and on a case-by-case basis to be classified and minor or major by the project team prior to database lock.

The categories of protocol deviations which will be reviewed and classified as major/minor include:

- Informed Consent/Assent
- Inclusion/Exclusion Criteria
- Concomitant Medication
- Use of prohibited medication
- Laboratory Assessment
- Study Assessments/Procedures
- Investigational Product
- Overdose/Misuse
- Visit Window
- Non-compliance
- Other

7.3 Demographics and Other Baseline Characteristics

Descriptive summaries of the demographic and other baseline characteristics will be completed for all patients in the Safety population by treatment group, dose, and overall. These tabulations will include the following variables:

- Demographics (age, gender, race, ethnicity, height, weight, and BMI)
- IO test (WASI-II)
- K-SADS-PL

Prior medication: The frequency and percentage of all prior medications will be summarized by Anatomical Therapeutic Chemical (ATC) classification level 3 and preferred term for all patients in the Safety population by treatment group and overall.

Medical History: Incidences of medical history will be listed by reported term for all patients in the Safety population.

All demographic and other baseline characteristics will be presented in subject listings.

SAP FINAL Version 2.0

7.4 Baseline Disease Characteristics

Descriptive summaries of baseline disease characteristics will be provided for all patients in the ITT population by treatment group and overall. These tabulations will include the following variables:

Page 16 of 88

- ADHD Subtype
- Age at Diagnosis
- Time Since ADHD Diagnosis
- ADHD-RS-5 Baseline Score (Overall and sub-scales)
- CGI-S Score at baseline

8 EFFICACY ANALYSIS

8.1 Primary Analysis

The primary efficacy endpoint will be the change in ADHD-RS-5 total score from Baseline to the end of treatment (e.g., Visit 8). For any subjects who discontinue the study prior to Visit 8, their last treated value of the ADHD-RS-5 will be used. That is, the LOCF method of imputation will be employed. The analysis will be performed on the ITT population using an analysis of covariance (ANCOVA) model. The model will use a residual (restricted) maximum likelihood (REML) estimation method and a standard variance components (VC) covariance structure, with treatment group (NFC-1 or placebo) as a fixed factor and baseline ADHD-RS-5 total score as a covariate. The null hypothesis is that there are no differences between the means of the two treatment groups. The hypothesis will be tested at a two-tailed alpha of 0.05. This analysis will be repeated for each of the scheduled visits for ADHD-RS-5 and summarized within the table. Descriptive summaries for actual and change from baseline values will be displayed along with the LS means, LS mean treatment difference, and 95% CIs of the treatment difference, and p-values by visit.

8.2 Secondary Analysis

Secondary analysis endpoints will include the following measurements (ASHS and SCARED treated as continuous measures):

- Improvement in CGI-I/CGI-S
- Change from baseline in ASHS total score
- Change from baseline in SCARED total score

When appropriate, the analysis for these endpoints will employ the same model and approach as in the primary analysis using an ANCOVA as specified above. Additionally, any subscales for the above primary/secondary endpoints will be included on their corresponding table for the total score (i.e. ADHD-RS-5 Inattention subscale, SCARED Generalized Anxiety, etc.). Please see Section 6.3 for a complete list of derived subscales and composite scores.

Results of the CGI-I assessment will be dichotomized and presented by count and frequency for each week of treatment. CGI-I scores of 1 (very much improved) or 2 (much improved)will be combined into a single category labeled 'Improved', and all other scores (3 [minimally improved] to 7 [very much worse]) will be combined into a single category labeled 'Not Improved'. The

SAP FINAL Version 2.0

observed frequencies of 'Improved' subjects will be compared using a chi-square analysis to test the hypothesis of no association between Improvement and Treatment at type I error rate of 5%.

Page 17 of 88

The CGI-S assessment will be presented similarly. CGI-S scores of 1 (Normal, not at all ill) or 2 (Borderline mentally ill) will be combined into a single category labeled 'Normal or Borderline mentally ill', and all other scores (3 [Mildly Ill] to 7 [Among the most extremely ill patients]) will be combined into a single category labeled 'Mentally ill'.

As to measure treatment response and remission of subjects, three criteria will be defined for each [4]. For response, the criteria are (A) a change in ADHD-RS-5 total score from baseline of 30% or more, (B) a CGI-I score of 1 (very much improved) or 2 (much improved) relative to baseline, and (C) a composite requiring both (A) and (B) to be met. For remission, the criteria are (A) ADHD-RS-5 total score of 18 or less at post-baseline visits, (B) a CGI-I score of 1, and (C) a composite of (A) and (B) to be met. The observed frequency and percentage of subjects in each category will be presented and will be compared using a chi-square analysis to test the hypothesis of no association between response/remission and treatment for each category.

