# 13.4.3.1 Primary Analysis

The primary analysis will focus on the effect of treatment on ADHD, as indicated by the ADHD-RS-5. The change in ADHD-RS-5 will be derived as the difference between the last post-treatment value and that recorded at the Baseline visit. The analysis of the change will employ a 1-way analysis of variance (ANOVA) model with a term for treatment (active or placebo). Depending on the fit of the single-factor model, subsequent exploratory analyses may be performed that include additional independent factors (eg, age, gender, and/or maintenance dose of study drug) as well as covariates that have been determined to be associated with experimental results (eg, baseline value of the dependent variable). Results of these exploratory analyses will be presented as estimates for all factors included in the model with corresponding 95% confidence intervals and associated levels of statistical significance.

This analysis will be performed with primary focus on the ITT Population.

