## 13.4.3.2 Secondary Analyses

Secondary efficacy analyses will examine the effects of the treatment on changes observed in other efficacy measures (ie, CGI-S, ASHS, and SCARED). These analyses will model the overall or total scale scores and will employ the same general approach as for the primary analysis. All secondary efficacy measures will be treated as continuous measurement scales and analyzed by the ANOVA methods described above.

Results of the CGI-I assessment will also be dichotomized and presented for each week of treatment. CGI-I scores of 1 or 2 will be combined into a single group labelled "Improved" and scores of 3 to 7 will be combined and labelled "No Improvement." The observed proportions of "Improved" subjects will be compared between treatment groups at each week of the study.

In addition, analysis of the weekly results from ADHD-RS-5 and CGI-I will be evaluated for evidence of trend over time. This analysis will employ a linear mixed-effects model with repeated measures on each subject. Terms for the model will be selected as described for the primary analysis.

Secondary analyses will focus on the ITT Population. However, analyses of the PP Population may be performed if warranted by the data.

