10 CHANGES FROM PLANNED ANALYSIS

Below are the major changes and/or updates from the protocol planned analysis:

- The SAP has ANCOVA with LOCF as the primary endpoint but this was noted as ANOVA in the protocol
- CGI-I and CGI-S were originally going to be analyzed by ANOVA, but will be analyzed by a Chi-Square test
- PCI analyses has been added for ECG, Vitals
- Post-treatment AEs and Post-treatment medications have been added
- Several tables now include dose group summaries instead of NFC-1 vs. Placebo

SAP FINAL Version 2.0

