11.2 Planned Table Shells

Table	Table Title	Topline
14.1.1	Disposition of Study Population by Optimized Dose and Randomized Treatment (ITT Population)	х
14.1.2	Major Protocol Deviations (ITT Population)	
14.1.3	Demographics and Baseline Characteristics by Optimized Dose and Randomized Treatment (Safety Population)	х
14.1.4	Disease Characteristics at Baseline by Optimized Dose and Randomized Treatment (Safety Population)	х
14.1.5	Summary of Prior Medications by Randomized Treatment (Safety Population)	
14.2.1.1	Analysis of Change from Baseline in ADHD-RS-5: Total Score and Subscales, by Study Visit (ITT Population)	х
14.2.1.2	Summary of Change from Baseline in ADHD-RS-5 Score and Subscales by Actual Dose and Randomized Treatment, by Study Visit (ITT Population)	
14.2.2.1	Chi-Square Analysis of CGI-I Improvement, by Study Visit (ITT Population)	х
14.2.2.2	Summary of Categorical and Continuous CGI-I Scores by Randomized Treatment Group and Study Visit (ITT Population)	х
14.2.2.3	Summary of CGI-I Improvement by Optimized Dose and Randomized Treatment, by Study Visit (ITT Population)	
14.2.3.1	Chi-Square Analysis of CGI-S Improvement, by Study Visit (ITT Population)	
14.2.3.2	Summary of Categorical and Continuous CGI-S Scores by Randomized Treatment Group and Study Visit (ITT Population)	
14.2.3.3	Summary of CGI-S Improvement by Optimized Dose and Randomized Treatment, by Study Visit (ITT Population)	
14.2.4.1	Analysis of Change from Baseline in ASHS Total Score and Factors, by Study Visit (ITT Population)	
14.2.4.2	Summary of Change from Baseline in ASHS Total Score and Factors by Randomized Treatment, by Study Visit (ITT Population)	
14.2.5.1	Analysis of Change from Baseline in SCARED Score and Factors, by Study Visit (ITT Population)	
14.2.5.2	Summary of Change from Baseline in SCARED Score and Factors by Randomized Treatment, by Study Visit (ITT Population)	
14.2.6.1	Chi-Square Analysis of Response and Remission Criteria, at End of Study (ITT Population)	х
14.3.1.1	Summary of TEAEs by Dose at Onset (Safety Population)	
14.3.1.2	Incidence of TEAEs by Dose at Onset and Randomized Treatment (Safety Population)	х
14.3.1.3	Incidence of TEAEs occurring in more than 5% of subjects by Randomized Treatment (Safety Population)	

SAP FINAL Version 2.0

14.3.1.4	Incidence of Post-Treatment AE's by Randomized Treatment (Safety Population)	
14.3.1.5	Incidence of SAE's by Randomized Treatment (Safety Population)	

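### The CGI-S 'Improvement' test classifies only the final score (1-2 versus 3-7), ignores baseline, and replaces the protocol's analysis of change without a stated reason

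*SAP*

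**What the plan says.** **Protocol.** Section 13.4.3.2 sets the aim for this scale: "Secondary efficacy analyses will examine the effects of the treatment on changes observed in other efficacy measures (ie, CGI-S, ASHS, and SCARED"). The method follows: "All secondary efficacy measures will be treated as continuous measurement scales and analyzed by the ANOVA methods described above". The method referred to is the model in 13.4.3.1, a one-way ANOVA of change with a treatment term. CGI-S is rated at Screening, at Baseline (Visit 2) and at Visit 8/ET (10.3.2.2 and the Schedule of Events), so there is one post-baseline rating.

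**SAP.** Section 8.2 names the endpoint "Improvement in CGI-I/CGI-S" and limits continuous treatment to two other scales: "ASHS and SCARED treated as continuous measures". For CGI-S it says "CGI-S scores of 1 (Normal, not at all ill) or 2 (Borderline mentally ill) will be combined into a single category", labelled 'Normal or Borderline mentally ill'; scores 3-7 are 'Mentally ill'. Section 10 records the change: "CGI-I and CGI-S were originally going to be analyzed by ANOVA, but will be analyzed by a Chi-Square test". No reason follows.

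The only inferential CGI-S table in the index (11.2) is Table 14.2.3.1, a chi-square titled as CGI-S improvement. Table 14.2.3.2 is descriptive and reuses the CGI-I summary shell, which has neither a change column nor a test. Baseline CGI-S appears only as a baseline characteristic (7.4 and Table 14.1.4).

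**The concern.** CGI-I is a rating of change, so scores 1-2 on it do mean improved. CGI-S is a rating of current severity, so the same split says only where the subject ends. SAP 8.2 carries the CGI-I presentation over to CGI-S and keeps the word improvement in the endpoint bullet and the table titles.

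A reader would take the p-value in Table 14.2.3.1 as a test of change. Many subjects who improve would sit in the unfavourable class, and a subject already at 1 or 2 at baseline would count as favourable without changing. As the tables are planned, change in CGI-S, which the protocol set out to test, is neither tested nor tabulated.

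**Working it through.** **1. The plan's own figure.** The SAP states no power for CGI-S. Its one power statement (5.1) concerns a comparison of mean change, which is taken here as the primary endpoint, with effect size 0.7. Normal approximation: power = Φ(0.7·√(n/2) − 1.96).
- 45 per arm: Φ(3.320 − 1.96) = 91.3% (90.7% by noncentral t).
- 40 per arm: Φ(3.130 − 1.96) = 87.9% (87.1% by noncentral t).

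This is roughly the stated 90%. The 0.7 is not used below as a CGI-S assumption.

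**2. What the split requires, from the documents alone.** The fall needed to reach class 1-2 is baseline − 2.

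| Baseline CGI-S | Fall needed |
|---|---|
| 1 or 2 | 0 |
| 3 | 1 |
| 4 | 2 |
| 5 | 3 |
| 6 | 4 |
| 7 | 5 |

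The only CGI-S data in the documents are the Phase 1b means in Protocol 5.2, which fell from 3.97 to 3.00, or 0.97 points, without a control group. A subject who goes from 4 to 3, close to that mean change, is 'Mentally ill' at both visits.

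**3. How many improvers are misplaced (illustration).** Assumed: normal baseline and endpoint, rounded and clipped to 1-7; active end mean 3.0 with SD 0.8-1.2; baseline mean 4.0-4.5 with SD 0.7-1.0; correlation r 0.3-0.5. The share of active subjects with a final score of 3-7 is:
- 50-70% among those who fall by at least 1 point;
- 23-62% among those who fall by at least 2 points.

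If the effect is instead concentrated in a subset of responders, the shares are 50-61% and 31-41%.

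**4. Power (illustration, 40 per arm, two-sided 0.05).**

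*Uniform shift:* end means 3.0 and 3.7, both SDs 1.0, r 0.3-0.5.
- Chi-square: p1 = Φ((2.5 − 3.0)/1.0) = 0.309 and p0 = Φ((2.5 − 3.7)/1.0) = 0.115, a difference of 0.193. The standard error is 0.0914 under the null and 0.0888 under the alternative. Power = Φ((0.193 − 1.96 × 0.0914)/0.0888) ≈ 56%. Simulation gives 57-59%.
- Change ANOVA: rounding adds 1/12 to each variance, so SD(change) = √(2 × 1.083 − 2r) = 1.252 at r = 0.3 and 1.080 at r = 0.5. Power = Φ(0.7·√20/SD − 1.96) = 71% and 83%. Simulation gives 70-82%.
- ANCOVA: residual SD = √(1.083 × (1 − (r/1.083)²)) = 1.000 and 0.923. Power = 88% and 92%. Simulation gives 87-92%.

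*Responder mixture:* baseline 4.5 (SD 1.0); placebo end mean 4.0 (SD 0.9-1.0); 30-35% of active subjects centred at 2.0 (SD 0.5-0.7) and the rest like placebo. Simulated power is chi-square 73-94%, ANCOVA 62-84% and change ANOVA 47-72%, so the order reverses.

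Under no effect the chi-square rejects in 4.9-5.9% of simulated trials.

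**The case against.** - **The switch is disclosed and pre-specified.** SAP 10 lists it, Protocol 13.4 leaves analytical detail to the SAP, and no other entry in SAP 10 carries a reason either. This stands. The missing reason is a gap in documentation, not a hidden change.
- **SAP 8.2 says the ANCOVA applies to the secondary endpoints when appropriate.** That could be read to include CGI-S. It does not rescue the plan: the same section limits continuous treatment to ASHS and SCARED, SAP 10 names chi-square, and no ANCOVA table for CGI-S is indexed.
- **The category is defined correctly in the text and in the shell footnote.** True. The misnomer is confined to the endpoint bullet and the table titles, but those are what a summary of results repeats.
- **Baseline scores of 1-2 are unlikely with ADHD-RS-5 of at least 28.** This stands. With baseline mean 4.0 and SD 1.0, Φ((2.5 − 4.0)/1.0) is about 7%; with mean 4.5 it is about 2%. No entry criterion sets a CGI-S minimum, but the improvers left in the unfavourable class are the larger problem.
- **An end state is a legitimate endpoint, and every split misplaces some improvers.** Also true. The SAP's remission criterion of ADHD-RS-5 at 18 or less is an end state too, but it is named as one.
- **Power does not clearly favour ANCOVA.** This stands, and the point does not rest on power.

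**Conclusion.** The concern holds. The test labelled CGI-S improvement measures a final state, leaves out a baseline value that is collected, and replaces the analysis of change the protocol planned, with no reason given. Type I error is not at issue, because randomisation makes the chi-square a valid test of the end state.

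The table of falls needed in step 2 follows from the documents alone. The misclassification shares and all power figures rest on assumed CGI-S means, SDs and correlations, and no general power ranking is claimed.

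The impact is limited to one ungated secondary endpoint. ADHD-RS-5, CGI-I and the response criteria still address change, and the primary conclusion is unaffected. The change should be made, but the trial's main result does not depend on it.

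**What to change.** 1. In SAP 8.2, make the CGI-S improvement test the ANCOVA of SAP 8.1 applied to change in CGI-S from Baseline to Visit 8/ET, with treatment and baseline CGI-S as terms. Report the LS mean difference and its 95% CI. State that it uses observed Visit 8/ET scores: there is no earlier post-baseline rating to carry forward, and SAP 6.2 imputes nothing beyond ADHD-RS-5.
2. Keep the 1-2 versus 3-7 split as supportive, and retitle its table 'Normal or borderline mentally ill at Visit 8/ET'.
3. Leave the CGI-I analysis as planned, since that scale already rates change.
4. In SAP 10, give the reason for whatever departure from the protocol's one-way ANOVA remains.

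The cost is SAP wording, one retitled table and one more run of a model already specified for ASHS and SCARED. No new data are needed. The small downside is that a 7-point ordinal scale is treated as continuous, which the protocol had already accepted.
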